12.5.3.2. Comparison of DLco/DLno gas diffusion parameters at baseline by group (HF, HV)

Tables

No.	Population	IDSL No. / Example Shell	Title	Additional Programming Notes	Responsibility	Deliverable Priority
11.6	Evaluable	DM1	Summary of gas diffusion, lung function parameters by visit.		Programmer	SAC
11.7	Evaluable	Example A	Analysis of gas diffusion parameters: parameters DLno, DLco, and DLno/DLco ratio at baseline.	Using mixed model to compare all parameters of interest between HF and HV if data permit.	Statistician	SAC

Figures

11.401	Evaluable	Example B	Mean (SE) Plot for gas diffusion (DLno, DLco and DLco/DLno) , lung function parameter	Separate line for HF and HV patients across 3 scans, a separate plot for each gas diffusion, lung function parameter	Programmer	SAC
11.501	Evaluable	Example C	Spaghetti plot of gas diffusion parameter by scan session (DLno, DLco and DLco/DLno)	Gas diffusion parameter on the vertical axes, scan session on the horizontal axes, and different symbols for HF and HV patients, a separate plot for each gas diffusion parameter	Programmer	SAC

12.5.3.3. Comparison of Dyspnoea Score at baseline by group (HV, HF)Tables

No.	Population	IDSL No. / Example Shell	Title	Additional Programming Notes	Responsibility	Deliverable Priority
11.8	Evaluable	DM1	Summary of Dyspnoea score by visit and session	Use dyspnoea variables at each planned time point, including immediately before and after both exercise tests.	Programmer	SAC

Figures

11.6	Evaluable	Example F	Frequency bar plot of Dyspnoea score by visit		Programmer	SAC
------	-----------	-----------	---	--	------------	-----

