5. ANALYSIS POPULATIONS

An evaluable subject is defined as a subject that has MRI data of sufficient quality to enable DCE-MRI modelling in both Session 1 and Session 2.

All enrolled population

The all enrolled population will include all subjects who have signed the informed consent for participation in the study.

Safety population

The safety population will include all enrolled subjects who have initiated Session 1 DCE-MRI scan. All safety analyses will be based on the safety population.

For Group 3, the safety population will include all enrolled subjects who have initiated at least one session of DCE-MRI or LUS scan.

This is the population to be used for all tables, listings, and figures of patients in group 3.

Evaluable population

The evaluable population will include subjects in safety population who are 40 years and older. There is no plan to exclude subjects with major or minor protocol deviations from the analyses. However, subject data will be examined for evidence of protocol deviations in order to assess how well the protocol was followed. If necessary, any decision to exclude any subject from the planned analyses will be determined when the database is released for reporting purposes.

The evaluable populations have been changed in this RAP amendment to limit the analysis populations to subjects with age greater than 40 years old at baseline. At the interim analysis, it was realized that age may confound the results in the HV population. Since HV and HF subjects were not age-matched, limiting the analysis population to similar age range will provide a more appropriate comparison. This analysis will exclude

4 subjects; however, the study has enrolled an additional 5 subjects who are >40 years old in order to have a sufficient number of subjects for comparison. However, in addition to the comparisons using the defined populations in this RAP, a sensitivity analysis for the comparison between two groups on the change from baseline in V_e will be performed using safety population with all subjects who have evaluable MRI data in either Sessions 1 or 2.

The evaluable population definition does not apply to ADHF patients to be included in group 3 summaries.

This population is not applicable to Group 3.

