9. SAFETY ANALYSES

The precise format and content of Safety figures, tables and listings are shown in Section [12.3](#) of the RAP.

The tables will use the “Safety” population unless otherwise specified.

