9.2. Other Safety Measures

9.2.1. Vital Signs

Vitals signs, including systolic blood pressure, diastolic blood pressure and heart rate, will be collected at screening, and after MRI scan in Sessions 1 and 2. In Session 3, data will also be collected at the beginning and at the end of the maximal exercise test and the constant workload exercise test. Descriptive statistics for the measurements in all sessions and change from pre-exercise will be provided.

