9.2.3. Dyspnoea score

Dyspnoea score will be collected after MRI scan in Sessions 1 and 2. In Session 3, data will also be collected before and after the maximal exercise test and the constant workload exercise test. Also data will be collected after MRI scan in constant workload visit. The dyspnoea score data is (0,1,2,3,4,5), descriptive statistics for the measurements

in all sessions and change from pre-exercise in session 3 will be provided, in addition a bar chart showing the frequency of each score will be presented.

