10. VALIDATION ANALYSES

Planned analyses for the primary, secondary and exploratory objectives of the study are described in this section using the evaluable population as the primary analysis population. Listings of all MRI data, clinical and biochemical measures will be produced. Special listings, such as listings that include data from multiple sources or include only a subset of subjects/measurements are described in the corresponding sections below.

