12.5.3.4. Comparison of Respiratory Rate at baseline by group (HV, HF)

Tables

No.	Population	IDSL No. / Example Shell	Title	Additional Programming Notes	Responsibility	Deliverable Priority
11.9	Evaluable	DM1	Summary of Respiratory rate by visit	Use respiratory rate at each planned time point.	Programmer	SAC

Figures

11.7	Evaluable	Example B	Mean (SE) Plot for respiratory rate by visit.	Separate line for HF and HV patients across 3 scans.	Programmer	SAC
------	-----------	-----------	---	--	------------	-----

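### For Groups 1 and 2, respiratory rate and dyspnoea are classed as safety measures but displayed only on the age-restricted Evaluable population, so four subjects appear in none of those displays

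*SAP*

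**What the plan says.** SAP section 5 sets the population rule without exception: "All safety analyses will be based on the safety population". It then defines the analysis set for the HF-HV work: "The evaluable population will include subjects in safety population who are 40 years and older". The reason given for the age limit is that age may confound results in the healthy volunteers, who were not age-matched to the HF subjects. Section 5 says the limit removes 4 subjects.

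Respiratory rate (9.2.2) and dyspnoea (9.2.3) come under "9.2. Other Safety Measures", within section 9, Safety Analyses. Both subsections promise descriptive statistics for all sessions and the Session 3 change from pre-exercise. For dyspnoea, "In Session 3, data will also be collected before and after the maximal exercise test and the constant workload exercise test". Section 9 makes Safety the default for its tables, with the qualifier "population unless otherwise specified".

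In the display list, dyspnoea is in 12.5.3.3 (Table 11.8, "Summary of Dyspnoea score by visit and session", and Figure 11.6) and respiratory rate in 12.5.3.4 (Table 11.9, "Summary of Respiratory rate by visit", and Figure 11.7). Their listings are 11.2 and 11.3, in 12.5.3.7. All of these fall under 12.5, Efficacy.

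**The concern.** The age limit was brought in to make the HF-HV imaging comparison fairer. That is no reason to leave out how a younger subject tolerated the scan or the exercise test, yet the display list applies the limit to both.

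The study has few other structured tolerability data. Adverse events are not routinely collected (protocol 6.12.2, SAP 9.1.2). In Groups 1 and 2 the ECG is done at screening only, and laboratory tests in Sessions 1 to 3 are for HF subjects only (protocol 6.1.1). Shortness of breath heads the side effects of bicycle testing in protocol Table 1, and Table 11.8 is where the scores before and after each exercise test are to be shown. If a subject under 40 became markedly breathless, these displays would not show it.

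**Working it through.** There is no calculation in the plan to reproduce. The check compares the population rules with the population column of the display list.

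**Step 1: displays of the two measures, Groups 1 and 2**

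| Display | Measure | SAP section | Population |
|---|---|---|---|
| Table 11.8 | Dyspnoea | 12.5.3.3 | Evaluable |
| Figure 11.6 | Dyspnoea | 12.5.3.3 | Evaluable |
| Table 11.9 | Respiratory rate | 12.5.3.4 | Evaluable |
| Figure 11.7 | Respiratory rate | 12.5.3.4 | Evaluable |
| Listing 11.2 | Dyspnoea | 12.5.3.7 | Evaluable |
| Listing 11.3 | Respiratory rate | 12.5.3.7 | Evaluable |

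Six of six are on Evaluable and none is on Safety.

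**Step 2: could a Safety display carry them under another title?** Section 12.3 covers MRI exposure and laboratory data; 12.4 covers vital signs and ECG. The vital signs outputs (Tables 10.5 and 10.6, Listing 10.5) are on Safety, but SAP 9.2.1 names only blood pressure and heart rate, and respiratory rate has its own subsection. Neither measure has an entry there.

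**Step 3: does another sentence restore the subjects?**
- The footnote to the 12.5.3.7 listings moves Group 3 displays to Safety. The age-based definition does not apply to Group 3, so this does not bring back the 4.
- Section 10 says "Listings of all MRI data, clinical and biochemical measures will be produced", but names Evaluable as its primary analysis population, and the display list puts Listings 11.2 and 11.3 on Evaluable.
- The Safety-population sensitivity analysis covers MRI measures only (v_e in section 5; v_e and k^trans in Table 11.2).

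**Step 4: the promised change scores.** For vital signs, Table 10.6 gives the change from pre-exercise. No display with that title exists for dyspnoea or respiratory rate in any population, although 9.2.2 and 9.2.3 promise it.

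**Step 5: size.** The 4 comes from SAP 5 and cannot be checked, because individual ages are not given. Every denominator below is an assumption.
- Planned 24 in Groups 1 and 2: 4/24 = 16.7%.
- Planned 24 plus the 5 added subjects: 4/29 = 13.8%.
- If all 4 are healthy volunteers, which section 5 suggests but does not state: 4/12 = 33.3% for the planned 12, or 4/17 = 23.5% if all 5 added subjects were also healthy volunteers.

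**The case against.** The strongest reply is that these are exploratory measures. The protocol's safety section (6.3) covers physical examination, vital signs, ECG and laboratory tests. Dyspnoea and respiratory rate have separate sections (6.5, 6.6) and are listed as correlates of the MRI measures. SAP 10.3.3 summarises both by group on the Evaluable population, and Tables 11.8 and 11.9 sit under headings that describe an HF-HV comparison, where the age restriction has the same logic as for MRI. Section 9 also lets the display list override its default for tables.

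Much of this stands. The Evaluable versions are legitimate exploratory displays and should remain. It does not meet the section 5 rule, which has no such escape, or supply the safety summary that 9.2.2 and 9.2.3 promise. The qualifier in section 9 also speaks only of tables, and the listings are restricted too.

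It is also fair that the 4 subjects do not vanish from safety reporting. Exposure, laboratory data, vital signs and ECG are on Safety. The SAP text also provides for a summary of SAEs and a listing, with reasons, of subjects who completed two scans but not the third.

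Two stronger readings are tempting, and the documents do not support them.
- A reader might infer that the excluded subjects' MRI data are also unlisted, because Listing 11.1 is on Evaluable. Listing 10.1 is on Safety and its programming note asks for all MRI data. Its title may mean exposure only, but as written it leaves no clear gap.
- A reader might tie the omission to the first risk in protocol Table 1, worsening dyspnoea when supine. That entry is limited to heart failure subjects, and the excluded subjects are probably healthy volunteers. Breathlessness on exercise is the relevant ground, and the documents do not say whether any of the 4 reached Session 3.

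**Conclusion.** The SAP is inconsistent on this point for Groups 1 and 2. It classes two measures as safety, requires safety analyses on the Safety population, and then displays both only on a subset chosen for another purpose. The 4 subjects removed by the age cut appear in none of the six indexed displays of dyspnoea or respiratory rate.

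The severity is minor. The readings are still collected, so the defect lies in reporting. The study gives no investigational product, and no primary or secondary estimate changes. The percentages illustrate scale only: enrolment totals and the group membership of the 4 are not documented.

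**What to change.** 1. Set Listings 11.2 and 11.3 to Safety for Groups 1 and 2, with a column flagging membership of the Evaluable population. Group 3 needs no change.
2. Add Safety-population summaries of dyspnoea and respiratory rate to section 12.4, including the Session 3 change from pre-exercise promised in 9.2.2 and 9.2.3.
3. Keep Tables 11.8 and 11.9 and Figures 11.6 and 11.7 on Evaluable, and label them as exploratory HF-HV displays.

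The cost is two population cells, one flag column and two added tables built on summaries already specified. No new data are needed.

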12.5.3.4. Comparison of Respiratory Rate at baseline by group (HV, HF)

Tables

No.	Population	IDSL No. / Example Shell	Title	Additional Programming Notes	Responsibility	Deliverable Priority
11.9	Evaluable	DM1	Summary of Respiratory rate by visit	Use respiratory rate at each planned time point.	Programmer	SAC

Figures

11.7	Evaluable	Example B	Mean (SE) Plot for respiratory rate by visit.	Separate line for HF and HV patients across 3 scans.	Programmer	SAC
------	-----------	-----------	---	--	------------	-----

12.5.3.5. Comparison of effect of exercise at Scan 3 by group (HV, HF)

Tables

No.	Population	IDSL No. / Example Shell	Title	Additional Programming Notes	Responsibility	Deliverable Priority
11.10	Evaluable	Example A	Analysis of effect of exercise (session 3) on gas diffusion parameters	Amend footnote to: Analysis performed using a mixed effect model, subject is random effect, (HF or HV) as fixed effects. With change from pre-exercise gas diffusion parameters DLno, DMco, for both exercise tests.	Statistician	SAC

12.5.3.6. Comparison of exercise test parameters at Scan 3 by group (HV, HF)Tables

No.	Population	IDSL No. / Example Shell	Title	Additional Programming Notes	Responsibility	Deliverable Priority
11.11	Evaluable	DM1	Summary of exercise test parameters	Use the data collected at scan 3, no pre/post or change from baseline values.	Programmer	SAC
11.12	Evaluable	Example A	Analysis of exercise test parameters of interest (Ve/Vco ₂ ratio at Scan 3 by HF and HV.	Use the data collected at scan 3, no pre/post or change from baseline values.	Statistician	SAC

12.5.3.7. Relationship between exercise parameters (Ve/Vco2) vs gas diffusion DLno/DLco parameters at scan 3

Listings

No.	Population ¹	IDSL No. / Example Shell	Title	Additional Programming Notes	Responsibility	Deliverable Priority
11.1	Evalauble		Listing of DCE-MRI scan data	Include all variables collected, i.e. interstitial volume, exchange rate, pulmonary edema and vascular permeability.	Programmer	SAC. Group 3 SAC
11.2	Evalauble		Listing of dyspnoea score	Include all variables collected.	Programmer	SAC, Group 3 SAC
11.3	Evalauble		Listing of respiratory rate	Include all variables collected.	Programmer	SAC, Group 3 SAC
11.4	Evalauble		Listing of NT-proBNP measurements	Include all variables collected.	Programmer	SAC, Group 3 SAC
11.5	Evalauble		Listing of exercise capacity measurements	Include all variables collected.	Programmer	SAC, Group 3 SAC
11.6	Evalauble		Listing of DLco and DLno measurements	Include all variables collected.	Programmer	SAC, Group 3 SAC
11.7	Evalauble		Listing of plasma volume (v_p)	Include all variables collected.	Programmer	SAC, Group 3 SAC
11.8	Evalauble		Listing of T_1 relaxation rate and proton density	Include all variables collected.	Programmer	SAC
11.7	Evalauble		Listing of Lung Ultrasound Data and Score	Include all variables collected, including B-line counts, total scores as well as by thoracic zones	Programmer	Group 3 SAC

¹ Evaluable population is not applicable to Group 3, using Safety population for Group 3 displays

12.6. Data Display Specifications (Example Shells)

Example : Example A Page 1 of n
 Protocol : 2013N186309_02
 Population : Completers

Table X.X

Analysis of contrast agent interstitial volume (v_e) and exchange rate (k^{trans}) data for total lung, left lung, right lung, left apical segments, right apical segment and left basal segments and right basal segment

Pls update this mock table with headers something as the following:

Parameter	Region	Comparisons (Grp1 vs Grp0)		LSMean (Se)		Point estimates	
		Group1	Group0	Group1	Group0	and 95% CI	p-value
Ve	Left Lung	HF (n=)	HV (n=)	xxx.xx(xx.x)	xxx.xx(xx.xx)	xx.xx(xx.xx, xx.xx)	0.xx
		Post Exercise	Session 2				
		in HF (n=)	in HF (n=)	xxx.xx(xx.x)	xxx.xx(xx.xx)	xx.xx(xx.xx, xx.xx)	0.xx

Example : Example A (Secondary Objective)

Protocol: 201137

Population: Evaluable

Page 1 of 6

Table 11.3
Analysis of within subject variability of DCE-MRI measures of pulmonary edema
and vascular permeability

Comparisons: (Session 2 Vs Session 1)

MRI test(Unit)	Region of interest	Population	GeoMean (Se in log)		Point estimates (Ratio) and 95% CI	Coef. of Variation		
			Session2	Session1		p-value	by pop	
Transfer rate from plasma to extracellu lar space (EES) (Ktrans) (1/MIN)	Lungs	Heart Failure (n=12)	0.187 (0.129)	0.206 (0.193)	0.908 (0.634, 1.300)	0.5789	32.4	43.3

Example : Example B

Protocol : 2013N186309_02

[figure not shown]
Population : Completers

Page 1 of n

Figure X.X

Mean (SE) Plot, Analysis performed using a Mixed effect model with subject (nested within scanning session) treated as a random effect, patient population (HF or HV) and Scanning Session (Session 1 and 2) as fixed

Page 1 of 1

[figure not shown]

effects

Page 1 of n

Example : Example C
Protocol : 2013N186309_02
Population : Completers

Figure X.X

[figure not shown]

Example : Example D
Protocol : 2013N186309_02
Population : Completers

Page 1 of n

Figure X.X

ApoA1 CH (%) at week 8 vs. Baseline NEFA (MEQ/L)

Amend title to "Scatter plot of var 1 vs var 2.

Amend axes labels to appropriate variable names

Amend legend text to Healthy Volunteers and Heart Failure patients.

Example: Example E

Protocol: 2013N186309_02

Population: Completers

Page 1 of n

Table xx.xx

Correlation of Change from Baseline in MRI Parameters and Change from Baseline NT-proBNP Analysis

	Parameter 1	Parameter 2	Group	Pearson's Correlation (P-value)	Spearman's Correlation (P-value)
Left Lung					
Apical segment	MRI Parameter	NT-proBNP Parameter	Healthy volunteers	x.xxxx (0.xxxx)	x.xxxx (0.xxxx)
	MRI Parameter	NT-proBNP Parameter	Heart failure	x.xxxx (0.xxxx)	x.xxxx (0.xxxx)
Basal segment	MRI Parameter	NT-proBNP Parameter	Healthy volunteers	x.xxxx (0.xxxx)	x.xxxx (0.xxxx)
	MRI Parameter	NT-proBNP Parameter	Heart failure	x.xxxx (0.xxxx)	x.xxxx (0.xxxx)
Total	MRI Parameter	NT-proBNP Parameter	Healthy volunteers	x.xxxx (0.xxxx)	x.xxxx (0.xxxx)
	MRI Parameter	NT-proBNP Parameter	Heart failure	x.xxxx (0.xxxx)	x.xxxx (0.xxxx)
Right Lung					

Apical segment	MRI Parameter	NT-proBNP Parameter	Healthy volunteers	x.xxxx (0.xxxx)	x.xxxx (0.xxxx)
	MRI Parameter	NT-proBNP Parameter	Heart failure	x.xxxx (0.xxxx)	x.xxxx (0.xxxx)
Basal segment	MRI Parameter	NT-proBNP Parameter	Healthy volunteers	x.xxxx (0.xxxx)	x.xxxx (0.xxxx)
	MRI Parameter	NT-proBNP Parameter	Heart failure	x.xxxx (0.xxxx)	x.xxxx (0.xxxx)
Total	MRI Parameter	NT-proBNP Parameter	Healthy volunteers	x.xxxx (0.xxxx)	x.xxxx (0.xxxx)
	MRI Parameter	NT-proBNP Parameter	Heart failure	x.xxxx (0.xxxx)	x.xxxx (0.xxxx)
Total both lungs	MRI Parameter	NT-proBNP Parameter	Healthy volunteers	x.xxxx (0.xxxx)	x.xxxx (0.xxxx)
	MRI Parameter	NT-proBNP Parameter	Heart failure	x.xxxx (0.xxxx)	x.xxxx (0.xxxx)

Example : Example D
Protocol : 2013N186309_02
Population : Evaluable

Page 1 of n

Frequency bar plot of Dyspnoea score by visit
